2. TRIAL OBJECTIVES AND ENDPOINTS

2.1 MAIN OBJECTIVES, PRIMARY AND SECONDARY ENDPOINTS

2.1.1 Main objectives

The main objectives of this trial are to investigate safety, tolerability and pharmacokinetics (PK) of BI 474121 in healthy male subjects following oral administration of single rising doses.

2.1.2 Primary endpoint

The primary endpoint for assessment of safety and tolerability of BI 474121 is the percentage of subjects with drug-related adverse events (SRD part).

The following pharmacokinetic parameters will be determined if feasible (BA part):

- AUC_{0-tz} (area under the concentration-time curve of the analyte in plasma over the time interval from 0 to the last quantifiable data point)
- C_{max} (maximum measured concentration of the analyte in plasma)

2.1.3 Secondary endpoint

[figure not shown]
The following pharmacokinetic parameters will be determined if feasible:

SRD part:

- AUC_{0-tz} (area under the concentration-time curve of the analyte in plasma over the time interval from 0 to the last quantifiable data point)
- C_{max} (maximum measured concentration of the analyte in plasma)

BA part:

- $AUC_{0-\infty}$ (area under the concentration-time curve of the analyte in plasma over the time interval from 0 extrapolated to infinity)

[figure not shown]

Proprietary confidential information © 2020 Boehringer Ingelheim International GmbH or one or more of its affiliated companies

[figure not shown]
2.2.2.1 Safety and tolerability

Safety and tolerability of BI 474121 will be assessed based on:

- AEs (including clinically relevant findings from the physical examination)
- Safety laboratory tests
- 12-lead ECG
- Continuous ECG monitoring (SRD part only)
- Vital signs (blood pressure, pulse rate, orthostatic test (SRD part only))

Proprietary confidential information © 2020 Boehringer Ingelheim International GmbH or one or more of its affiliated companies

3. DESCRIPTION OF DESIGN AND TRIAL POPULATION

3.1 OVERALL TRIAL DESIGN AND PLAN

SRD part

This single-rising dose trial is designed as single-blind within dose groups, randomised, and placebo-controlled within parallel dose groups.

It is planned to include 56 healthy male subjects in this part of the trial. The subjects will be assigned to 7 groups consisting of 8 subjects per group; the groups will be dosed sequentially (see Table [3.1: 1](#)). The investigator is allowed to alter the scheduled dose groups (e.g., add low and/or intermediate dose groups) on the basis of experience gained during the study (for instance, based on preliminary PK data), provided the planned and approved highest dose is not exceeded. Thus, the actual number of subjects entered may be more than 56, but is not to exceed 72. Such changes may be implemented via non-substantial CTP amendments. The addition of further dose groups exceeding the already tested dose levels for the evaluation of safety findings is subject to a substantial CTP amendment requiring approval.

Within each dose group, 6 subjects will receive BI 474121 and 2 will receive placebo. Only one dose is tested within each dose group. For safety reasons, each dose group will consist of 3 cohorts.

The trial medication will be administered in the following order: For the first 4 subjects (cohort 1 and 2) the treatment order will be ‘active’ – ‘placebo’ – ‘active’ – ‘active’, while the following 4 subjects (cohort 3) will be randomised to 3x ‘active’ and 1x ‘placebo’

The second subject on active per dose group will be treated not earlier than 22 hours after the first subject on active (minimum time interval between 1st subject of cohort 1 [sentinel subject] and 1st of cohort 2). This is expected to be sufficient to detect relevant acute effects of BI 474121 in the sentinel subject based on an anticipated half-life of BI 474121 of approximately 19 hours prior to exposing more volunteers to BI 474121 at the respective dose level. In all cohorts, a time interval of at least 10 min will be maintained between dosings of individual subjects.

The dose groups to be evaluated are outlined in Table 3.1: 1 below.

Table 3.1: 1

Dose groups

Dose Group	1	2	3	4	5	6	7
Dose (mg)	0.25	1	2.5	5	10	20	40
Number of subjects	8	8	8	8	8	8	8
Subjects receiving placebo	2	2	2	2	2	2	2
Subjects receiving BI 474121	6	6	6	6	6	6	6

The dose groups will be dosed consecutively in ascending order, and a time interval of at least 3 days will be maintained between the last drug administration to subjects in the previous dose group and the first drug administration to subjects in the subsequent dose group. Moreover, a time interval of at least 7 days will be maintained for DG 1 to 3 and 14 days for DG 4 to 7 between the first drug administration to subjects in the previous dose group and the first drug administration to subjects in the subsequent dose group. The decision to treat the next dose group will be based upon safety, tolerability and pharmacokinetic data (for details refer to Section [7.4](#)) of the preceding dose groups. The next dose group will only be treated if, in the opinion of the investigator, no safety concerns have arisen in the preceding dose groups (i.e. no dose-limiting events occurred), and if none of the pre-specified trial-specific stopping criteria have been met (refer to Section [3.3.4.2](#)).

A documented safety review must take place prior to each dose escalation. Furthermore, an unscheduled safety review meeting can be requested anytime by the Principal Investigator (or an authorised deputy) or the sponsor of the study (for instance, due to the occurrence of any unforeseen adverse events).

Although no formal Safety Review meeting will take place within a given dose group, safety will be continuously monitored during this trial, and an individual will only be dosed in the absence of any safety concern (i.e. no dose-limiting events occurred) and if none of the pre-specified trial-specific stopping criteria have been met (refer to Section 3.3.4.2).

At minimum, data from 4 subjects on active drug need to be available for escalation to a higher dose. For the minimum dataset with regards to preliminary PK data, see Section 7.4. The minimum data set for review consists of the following:

- AEs in the current and preceding dose groups up to at least 48 h post dosing, including clinically relevant findings from ancillary safety testing listed below (Note: AEs may be ongoing at the time of Safety Reviews and AE information may be subject to change prior to Database Lock)
- Results from 12-lead ECG and continuous ECG monitoring in the current and preceding dose groups up to at least 24 h (DG 1 to 3) or 48 h (DG 4 to 7) post dosing
- Vital signs and results from the orthostatic tests in the current and preceding dose groups up to at least 24 h post dosing
- Clinical laboratory tests in the current and preceding dose groups up to 24 h post dosing
- Preliminary PK data for the selected time as per Section 7.4

- Check of criteria for stopping subject treatment as per Section [3.3.4.1](#)

The decision to escalate the dose will be made jointly by the Principal Investigator (or an authorised deputy) and the Clinical Trial Leader (or an authorised deputy) after in-depth analysis of all available safety data, especially SAEs (if occurred), AEs, and out-of-range laboratory results (if considered clinically significant). In addition and depending on the results and findings, suitable experts from the sponsor or external institutions may be consulted on an as needed basis. In these cases expert recommendations will be documented in the minutes of the Safety Review and considered for the decision making. Dose escalation will only be permitted if no safety concerns exist neither in the opinion of the Principal Investigator (or an authorised deputy) nor the Clinical Trial Leader (or an authorised deputy).

Safety Reviews can be conducted face-to-face or by video/telephone conference. The Clinical Trial Leader is responsible for the organisation and minutes of the reviews. Minutes will be signed off by the Principal Investigator (or an authorised deputy) and Clinical Trial Lead (or an authorised deputy), and will be filed in the ISF and TMF.

BA part

The BA part will be performed as randomised, open-label, three-way, six-sequence, cross-over trial in healthy male subjects in order to assess (1) the relative bioavailability of the tablet relative to PfOS (both administered under fasted conditions) and (2) the relative bioavailability of the tablet administered under fed and fasted conditions. The subjects will be randomly allocated to the 6 treatment sequences. The treatments will be one 2.5 mg or one 10 mg tablet administered in the fasting and fed state, after a standardised high-fat, high-calorie breakfast, as well as 2.5 mg or 10 mg PfOS administered in the fasting state. For details refer to Section [4.1.4](#).

There will be a wash out period of at least 7 days between the treatments.

A total of 12 healthy male subjects is planned to participate in the BA part.

An overview of all relevant activities is provided in the [Flow Chart](#). For visit schedule and details of trial procedures at selected visits, refer to Sections [6.1](#) and [6.2](#), respectively.

3.2 DISCUSSION OF TRIAL DESIGN, INCLUDING THE CHOICE OF CONTROL GROUP

SRD part:

For single-rising dose trials, the sequential rising dose design described in Section [3.1](#) is viewed favourably under the provision not to expose the subjects involved to undue risks.

Single-blind conditions regarding the subject's treatment (active or placebo) are maintained within each dose group. However, subjects and investigators will be aware of the dose of drug administered. The disadvantage of the trial design is a possible observer bias with regard to the dose-dependent effects; in addition, the sequential dosing of groups could potentially result in time-related effects. However, as such effects are expected to be small relative to the differences between the doses in the broad range investigated, unbiased comparisons between treatments can still be expected.

Proprietary confidential information © 2020 Boehringer Ingelheim International GmbH or one or more of its affiliated companies

It is standard in single or multiple rising dose trials involving healthy volunteers to include a placebo group to control for safety and tolerability of the trial medication. Each dose group consists of 8 subjects, with 6 on active treatment and 2 on placebo. For data analysis purposes, the placebo control group will include all subjects of all dose groups treated with placebo. Six subjects per active treatment group are generally considered to be sufficient for the exploratory evaluation of pharmacokinetics.

BA part:

For relative bioavailability trials, the cross-over design is preferred due to its efficiency: since each subject serves as his own control, the comparison between formulations or treatments is based on a comparison within subjects rather than between subjects. This trial design therefore removes intersubject variability from the comparison between formulations or treatments [cf. [R94-1529](#)].

3.3 SELECTION OF TRIAL POPULATION

It is planned that 56 healthy male subjects will enter the SRD part and 12 subjects the BA part of the study. In the SRD part, the actual number of subjects entered may exceed 56 subjects if additional intermediate or lower doses are tested (see Section [3.1](#)). Subjects will be recruited from the volunteers' pool of the trial site. Subjects can only participate either in the SRD or in the BA part of the trial.

Only male subjects will be included in the trial because no data on reproductive toxicology are available at this time.

A log of all subjects enrolled into the trial (i.e. who have signed informed consent) will be maintained in the ISF irrespective of whether they have been treated with investigational drug or not.

3.3.1 Main diagnosis for trial entry

The study will be performed in healthy subjects.

3.3.2 Inclusion criteria

Subjects will only be included in the trial if they meet the following criteria:

1. Healthy male subjects according to the assessment of the investigator, as based on a complete medical history including a physical examination, vital signs (BP, PR), 12-lead ECG, and clinical laboratory tests
2. Age of 18 to 45 years (inclusive)
3. BMI of 18.5 to 29.9 kg/m² (inclusive)
4. Signed and dated written informed consent prior to admission to the study, in accordance with GCP and local legislation

3.3.3 Exclusion criteria

Subjects will not be allowed to participate, if any of the following general criteria apply:

1. Any finding in the medical examination (including BP, PR or ECG) deviating from normal and assessed as clinically relevant by the investigator
2. Repeated measurement of systolic blood pressure outside the range of 100 to 140 mmHg, diastolic blood pressure outside the range of 50 to 90 mmHg, or pulse rate outside the range of 50 to 90 bpm
3. Any laboratory value outside the reference range that the investigator considers to be of clinical relevance
4. Any evidence of a concomitant disease assessed as clinically relevant by the investigator
5. Gastrointestinal, hepatic, renal, respiratory, cardiovascular, metabolic, immunological or hormonal disorders
6. Cholecystectomy or other surgery of the gastrointestinal tract that could interfere with the pharmacokinetics of the trial medication (except appendectomy or simple hernia repair)
7. Diseases of the central nervous system (including but not limited to any kind of seizures or stroke), and other relevant neurological or psychiatric disorders
8. History of relevant orthostatic hypotension, fainting spells, or blackouts
9. Chronic or relevant acute infections
10. History of relevant allergy or hypersensitivity (including allergy to the trial medication or its excipients)
11. Use of drugs within 30 days of planned administration of trial medication that might reasonably influence the results of the trial (including drugs that cause QT/QTc interval prolongation)
12. Intake of an investigational drug in another clinical trial within 60 days of planned administration of investigational drug in the current trial, or concurrent participation in another clinical trial in which investigational drug is administered
13. Smoker (more than 10 cigarettes or 3 cigars or 3 pipes per day)
14. Inability to refrain from smoking on specified trial days
15. Alcohol abuse (consumption of more than 24 g per day)
16. Drug abuse or positive drug screening
17. Blood donation of more than 100 mL within 30 days of planned administration of trial medication or intended blood donation during the trial
18. Intention to perform excessive physical activities within one week prior to the administration of trial medication or during the trial
19. Inability to comply with the dietary regimen of the trial site
20. A marked baseline prolongation of QT/QTc interval (such as QTc intervals that are repeatedly greater than 450 ms or any other relevant ECG finding at screening)

Proprietary confidential information © 2020 Boehringer Ingelheim International GmbH or one or more of its affiliated companies

21. A history of additional risk factors for *Torsade de Pointes* (such as heart failure, hypokalaemia, or family history of Long QT Syndrome)
22. Subject is assessed as unsuitable for inclusion by the investigator, for instance, because the subject is not considered able to understand and comply with study requirements, or has a condition that would not allow safe participation in the study
23. Male subjects with WOCBP partner who are unwilling to use a highly effective method of birth control from time point of administration of trial medication until 30 days thereafter. Highly effective methods of birth control are:
 - Male subject is sexually abstinent
 - Male subjects is vasectomised (vasectomy at least 1 year prior to enrolment), *plus* condom in male subject
 - Use of intrauterine device (IUD) or intrauterine hormone-releasing system (IUS)
 - Use of progestogen-only hormonal contraception by female partner that inhibits ovulation (only injectables or implants), *plus* condom in male subject
 - Use of combined (estrogen and progestogen containing) hormonal contraception by female partner that prevents ovulation (oral, intravaginal or transdermal), *plus* condom in male subject
 - Female partner is surgically sterilised (including hysterectomy)
 - Female partner is postmenopausal, defined as no menses for 1 year without an alternative medical cause (in questionable cases a blood sample with FSH above 40 U/L and estradiol below 30 ng/L is confirmatory)
- Sperm donation is not allowed from the time point of drug administration until 30 days thereafter.
24. ALT (alanine transaminase), AST (aspartate transaminase), or serum creatinine exceed upper limit of normal range at screening, confirmed by a repeat test
25. Orthostatic hypotension during orthostatic testing at Day -3, that the investigator considers to be of clinical relevance (only applicable for SRD part).
26. During COVID-19 pandemic: laboratory test indicative of an ongoing SARS-CoV-2 infection.

For study restrictions, refer to Section [4.2.2](#).

3.3.4 Withdrawal of subjects from treatment or assessments

Subjects may discontinue trial treatment or withdraw consent to trial participation as a whole ('withdrawal of consent') with very different implications; please see Sections 3.3.4.1 and [3.3.4.2](#) below.

If a subject is removed from or withdraws from the trial prior to the first administration of trial medication, the data of this subject will not be entered in the case report form (CRF) and will not be reported in the clinical trial report (CTR). If a subject is removed from or withdraws from the trial after the first administration of trial medication, this will be documented and the reason for discontinuation must be recorded in the CRF; in addition, the data will be included in the CRF and will be reported in the CTR.

Proprietary confidential information © 2020 Boehringer Ingelheim International GmbH or one or more of its affiliated companies

At the time of discontinuation, a complete end of trial examination will be performed, if possible, and the information will be recorded in the CRF. If the discontinuation occurs before the end of the REP (see Section [1.2.6](#)), the discontinued subject should if possible be questioned for AEs and concomitant therapies at or after the end of the REP in order to ensure collection of AEs and concomitant therapies throughout the REP, if not contrary to any consent withdrawal of the subject.

Since the risks of drug exposure of a (pregnant) female partner of a male study participant via the seminal fluid are yet unknown, adequate contraception as outlined in Section [3.3.2](#) is a prerequisite for participation in the study.

3.3.4.1 Discontinuation of trial treatment

An individual subject will discontinue trial treatment if:

1. The subject wants to discontinue trial treatment, without the need to justify the decision
2. The subject has repeatedly shown to be non-compliant with important trial procedures and, in the opinion of both, the investigator and sponsor representative, is not willing or able to adhere to the trial requirements in the future
3. The subject needs to take concomitant medication that interferes with the investigational medicinal product or other trial treatment
4. The subject can no longer receive trial treatment for medical reasons (such as surgery, adverse events [AEs], or diseases)
5. The subject has an elevation of AST and/or ALT ≥ 3 -fold ULN and an elevation of total bilirubin ≥ 2 -fold ULN (measured in the same blood sample) and/or needs to be followed up according to the DILI checklist provided in the ISF
6. The subject has a serious adverse reaction or a severe non-serious adverse reaction (applies to BA part).

In addition to these criteria, the investigator may discontinue subjects at any time based on his or her clinical judgment.

Even if the trial treatment is discontinued, the subject remains in the trial and, given his/her agreement, will undergo the procedures for early treatment discontinuation and follow up as outlined in the [Flow Chart](#) and section [6.2.3](#).

3.3.4.2 Withdrawal of consent to trial participation

Subjects may withdraw their consent to trial participation at any time without the need to justify the decision. If a subject wants to withdraw consent, the investigator should be involved in the discussion with the subject and explain the difference between trial treatment discontinuation and withdrawal of consent to trial participation, as well as explain the options for continued follow up after trial treatment discontinuation, please see section [3.3.4.1](#) above.

Proprietary confidential information © 2020 Boehringer Ingelheim International GmbH or one or more of its affiliated companies

3.3.4.3 Discontinuation of the trial by the sponsor

Boehringer Ingelheim reserves the right to discontinue the trial at any time for any of the following reasons (#5, #6 and #7 mandatory discontinuation criteria) :

1. Failure to meet expected enrolment goals overall or at a particular trial site
2. New toxicological findings, serious adverse events, or any safety information invalidating the earlier positive benefit-risk assessment.
3. Violation of GCP, or the CTP impairing the appropriate conduct of the trial.
4. The sponsor decides to discontinue the further development of the investigational product
5. Dose escalation in the SRD part or treatment in the BA part will be stopped if at least 2 subjects on active treatment at one dose level (SRD part) or 2 subjects in the BA part have relevant individual QT prolongations, i.e. a QTc increase of greater than 60 ms from baseline and/or an absolute QT or QTc greater than 500 ms, as confirmed by a repeat ECG recording.
6. Dose escalation in the SRD part will be stopped, if the C_{max} or AUC_{0-24} of at least 1 subject of one dose group increases above the following exposure thresholds or if the estimated gMean exposure is expected to exceed a C_{max} of 657 nM or an AUC_{0-24} of 6,201 nM*h. In this case, one or two additional dose levels lower than the planned next dose level may be given, as long as the expected gMean exposure values of the interim dose do not exceed these exposure thresholds. Estimation will be done based on preliminary PK results of preceding dose groups (see Section [7.4](#))
7. Occurrence of severe non-serious adverse events considered as drug-related by the investigator in 2 subjects of the same dose group (8 subjects) in the SRD part, or 3 subjects of the BA group (12 subjects), or occurrence of at least one drug-related serious adverse event. Moreover, dose escalation in the SRD part will be terminated if more than 3 of the actively dosed subjects at one dose level show drug-related and clinically relevant adverse events of at least moderate intensity.

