For this trial, a 40 mg dose has been selected as maximum dose. This dose is predicted to result in a C_{max} of 285 nM and AUC_{0-24} of 2,850 nM*h in humans. These exposures are 4.2-fold (C_{max}) and 4.0-fold (AUC_{0-24}) below the exposure caps defined above (see Section [1.3.2.1](#)) and the 40 mg dose will only be administered if predicted geometric mean values of C_{max} or AUC_{0-24} do not exceed the defined exposure limits, otherwise dose escalation will be stopped at lower doses.

A dose of 40 mg is predicted to result in exposures that are 4.2-fold (C_{max}) and 4-fold (AUC_{0-24}) below the exposures achieved in rats at NOAEL and 15.3-fold (C_{max}) and 12.6-fold (AUC_{0-24}) below the exposures achieved in Cynomolgus monkey at NOAEL.

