1.3.3 Escalation scheme (SRD part)

1.3.3.1 Escalation scheme (guided by preliminary PK analysis (see Section [7.4](#)))

Escalation scheme has been chosen such that the assumed therapeutic dose is reached at the third dose level with higher escalation factors (not more than 4-fold) at the lower dose levels and not more than 2-fold at the higher dose levels.

Table 1.3.3.1: 1 shows the planned dose escalation, the escalation factors, and the predicted systemic exposures. These are calculated based on predicted therapeutic exposures (see Section [1.2.2](#)) assuming linear kinetic.

Table 1.3.3.1: 1 Dose escalation scheme, escalation factors and BI 474121 exposure in plasma predicted based on preclinical data

Dose level [#]*	Dose of BI 474121 [mg]	Escalation factor from previous dose level	Predicted C_{max} [nM]	Predicted AUC_{0-24} [nM*h]
1	0.25		1.78	17.8
2	1	4.0	7.12	71.2
3	2.5	2.5	17.8	178.1
4	5	2	35.6	356.2
5	10	2	71.25	712.5
6	20	2	142.5	1,425
7	40	2	285	2,850

* A dose level (= dose group) will only be administered if the treatment in the preceding dose group(s) was safe and showed acceptable tolerability and if the systemic exposure of the next dose (gMean values for AUC_{0-24} and C_{max} , guided by preliminary PK analysis) is expected to not exceed the maximum acceptable exposure (see Section [1.3.2.1](#)). Moreover, dose escalation will be stopped in case individual observed exposure values in one subject exceed the maximum acceptable exposure. For escalations up to dose level 2 (inclusive), preliminary PK data are not needed (see also Section 7.4).

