1.3.3.2 Preliminary PK analysis

Dose escalation will be guided by preliminary PK analysis with the following aims:

- Ascertaining that adequate exposures are reached in this trial as a basis for further development of BI 474121,
- Ascertaining that the expected gMean exposure values of the next dose group do not exceed the maximum acceptable exposure in order to protect subjects' safety, and
- Ascertaining that dose escalation is stopped in case observed exposure values of a single subject exceed the maximum acceptable exposure.

For details, see Sections [3.3.4.3](#) and 7.4.

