1.4.3 Drug-related risks and safety measures

Factors of risk may derive from particular knowledge or the lack thereof, regarding (1) the mode of action, (2) the nature of the target, (3) the relevance of animal models and/or (4) findings in non-clinical safety studies.

Safety measures

The following safety measures will be applied in order to minimise the risk for healthy volunteers:

- Dose selection is based on a sound preclinical package including 4-week toxicological studies (see Section [1.2.3](#)) and non-clinical pharmacology data (Section [1.2.1](#)).

Proprietary confidential information © 2020 Boehringer Ingelheim International GmbH or one or more of its affiliated companies

- Careful selection of starting dose in the SRD part of the trial as described in Section [1.3](#).
- Dose escalation in the SRD part of the trial will be shallow with an increase of no more than 2-fold beyond the predicted human therapeutic dose of 2.5 mg of BI 474121.
- Measurement of BI 474121 plasma concentrations and preliminary determination of PK parameters in the SRD part of the trial (C_{max} , AUC_{0-24} , see Section [7.3.4](#)). For precautionary reasons, drug plasma concentrations in this healthy volunteer trial will not exceed the geometric mean (gMean) C_{max} of 657 nM for C_{max} and 6,201 nM*h for AUC_{0-24} (see Section [2.1](#)). Dose escalation will be stopped if the C_{max} or AUC_{0-24} of at least 1 subject of one dose group exceeds or if the estimated systemic exposure (group gMean values) of the next dose level is expected to exceed the maximum acceptable exposure (see Section 7.3.4).
- For safety reasons, each dose group of 8 subjects (6 on active, 2 on placebo) in the SRD part of the trial will be divided in three cohorts with staggered inclusion of subjects (see Section [3.1](#) for details). The first drug administration of cohort 2 and the first drug administration of cohort 3 will be no earlier than 22 hours after first drug administration in the previous cohort. Within each cohort, drug administrations will be separated by at least 10 min. This design ensures that between first and second active dose of each dose level there is a time interval of at least 22 hours. This time interval is expected to be sufficient to detect relevant first acute effects of BI 474121. In the BA part of the trial, 12 subjects will be dosed in one cohort with no minimum time interval defined between dosing.

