7.4 INTERIM ANALYSES

SRD part:

A preliminary analysis of PK parameters (AUC_{0-24} and C_{max} of BI 474121) provided as individual values and geometric means of the first cohort per dose level, will be performed for

- Dose level 1 before proceeding to dose level 3 (n+2)

Proprietary confidential information © 2020 Boehringer Ingelheim International GmbH or one or more of its affiliated companies

- Dose levels 3, 4, 5 and 6 (n) before proceeding to the next dose level 4, 5, 6, and 7 (n+1)

(Note: Data from the first cohorts of the above mentioned dose levels will be sufficient as long as the data from at least 2 subjects on active treatment were available.)

The pharmacokinetic parameters AUC_{0-24} and C_{max} for BI 474121 will be calculated according to the BI SOP 'Standards and processes for analyses performed within Clinical Pharmacokinetics/Pharmacodynamics' ([001-MCS-36-472](#)). The non-compartmental analysis will be performed using a validated software program such as Phoenix WinNonlin™ software (version 6.3 or higher, [REDACTED]) or SAS® Version 9.4 (or later version). A quality check of the preliminary data will be performed.

Available information on dose linearity from preceding dose groups will be considered when estimating C_{max} and AUC_{0-24} values to be expected for the next higher dose to be administered.

In contrast to the final PK calculations, the preliminary analysis will be based on planned sampling times rather than on actual times, regardless of whether actual times were within the time windows. Therefore, minor deviations may occur between preliminary and final results. The preliminary analysis will provide individual and mean concentration/effect-time profiles and summary statistics of individual values without subject identification information. The preliminary results will be distributed to the investigator and the trial team.

Depending on the results of available preliminary PK analyses and the tolerability and safety of the compound, changes to the dosing schedule (e.g., additional intermediate doses,) and additional PK/PD preliminary analysis may be performed if requested by the Trial Clinical Monitor, the investigator, or Trial Clinical Pharmacokineticist. Preliminary PK results will not be reported in the CTR.

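### Stopping criterion #6 (Protocol 3.3.4.3) does not say which trigger its exception follows, so it can be read to allow 30 mg after one subject exceeds an exposure threshold at 20 mg

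*Protocol*

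**What the plan says.** Protocol 3.3.4.3 lists #6 among the mandatory discontinuation criteria. Two triggers, joined by 'or', stop escalation in the SRD part:

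- **Individual trigger:** the Cmax or AUC0-24 of at least one subject in a dose group is above the thresholds.
- **gMean trigger:** the estimated gMean is expected to exceed 657 nM (Cmax) or 6,201 nM*h (AUC0-24).

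The next sentence is the exception: "In this case, one or two additional dose levels lower than the planned next dose level may be given". It applies as long as the expected gMean of the interim dose stays within the thresholds. No condition on individual values is attached.

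Three other places state the single-subject stop with no exception:

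- 1.3.3.1, table footnote: "dose escalation will be stopped in case individual observed exposure values in one subject exceed the maximum acceptable exposure".
- 1.3.3.2: "Ascertaining that dose escalation is stopped in case observed exposure values of a single subject exceed the maximum acceptable exposure". This section refers to 3.3.4.3 and 7.4 for details.
- 1.4.3: "Dose escalation will be stopped if the C_{max} or AUC_{0-24} of at least 1 subject of one dose group exceeds". The sentence runs on to the gMean trigger and words the limit as the maximum acceptable exposure. The sentence before it says that plasma concentrations "will not exceed the geometric mean (gMean) C_{max} of 657 nM for C_{max} and 6,201 nM*h for AUC_{0-24".

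The 1.3.3.1 footnote refers the maximum acceptable exposure to Section 1.3.2.1, which is not in the public text. The Synopsis names 30 mg as a possible intermediate dose. Section 7.4 lets the preliminary PK review rest on few subjects; first-cohort data "will be sufficient as long as the data from at least 2 subjects on active treatment were available".

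**The concern.** 'In this case' can refer to the stop as a whole, and so to both triggers, or only to the gMean clause just before it. The two readings give opposite answers when one subject on 20 mg is above a threshold and the group gMean is moderate. The narrow reading stops there. The broad reading allows 30 mg, which is lower than the planned 40 mg but higher than the dose that produced the breach.

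At stake is the protection of individual volunteers in a first-in-human trial. The individual trigger exists because a group mean can look acceptable while one person is highly exposed. On the broad reading, a test of the group mean alone would then decide whether the next group receives a higher dose.

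**Working it through.** **Inputs.** Table 1.3.3.1: 1 predicts 142.5 nM and 1,425 nM*h at 20 mg, and 285 nM and 2,850 nM*h at 40 mg, assuming linear kinetics. The thresholds in #6 are 657 nM and 6,201 nM*h. Linear scaling from 40 mg reproduces the table: 285 × 20/40 = 142.5 and 2,850 × 20/40 = 1,425.

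**How far exposure must exceed prediction.** 657/142.5 = 4.61 (Cmax) and 6,201/1,425 = 4.35 (AUC0-24) for one subject at 20 mg.

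**When the gMean condition still allows 30 mg.** The 20 mg gMean must be at most 657 × 20/30 = 438 nM and 6,201 × 20/30 = 4,134 nM*h. For 40 mg the limits are 657/2 = 328.5 nM and 6,201/2 = 3,100.5 nM*h.

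**Example 1, six on active drug, Cmax.** One subject has 700 nM and five have 250 nM. The gMean is (700 × 250^5)^(1/6) = 297 nM. The forecast is 1.5 × 297 = 445 nM at 30 mg and 2 × 297 = 594 nM at 40 mg. Only the individual trigger fires. The narrow reading stops; the broad reading allows 30 mg.

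**Example 2, the two-subject minimum of 7.4.** Values of 700 and 270 nM give a gMean of √(700 × 270) = 435 nM, so 652 nM is forecast at 30 mg and 869 nM at 40 mg. Both triggers fire. Even a reader who ties the exception to the gMean trigger could then invoke it, despite the individual breach.

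**How often.** The documents give no between-subject variability, so I assume a gCV of 30% or 50%. Model: ln Cmax is normal with mean ln(142.5 × m) and variance ln(1 + gCV²), where m is true over predicted exposure. Event: at least one subject is above 657 nM and 1.5 × gMean is at most 657 nM. The two-subject figures are by numerical integration, the others by simulation.

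| m | On active drug | gCV 30% | gCV 50% |
|---|---|---|---|
| 1 | 2 | <0.01% | 0.1% |
| 1.5 | 2 | 0.01% | 1.1% |
| 2 | 2 | 0.2% | 2.9% |
| 2.5 | 2 | 0.6% | 4.0% |
| 2 | 3 | 0.5% | 7.5% |
| 2 | 6 | 1.3% | 20% |

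Three is the number on active drug in cohorts 1 and 2 (Protocol 3.1). At m = 1 with six on active drug and gCV 50%, the chance of any breach is 0.36%.

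**How well the gMean condition protects.** At m = 2 (gCV 30% / 50%), the share of breaches that leave 30 mg allowed is 42% / 38% with two on active drug, 81% / 67% with three and 99% / 95% with six. With few subjects the outlier raises the gMean and often blocks 30 mg by itself; with six it hardly does. If the true 20 mg gMean were 328.5 nM, at least one of six would exceed 657 nM with probability 5% to 36% at 20 mg, and 66% to 85% at 30 mg (gCV 30% to 50%).

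**Which limit the other sections mean.** Section 1.3.2.2 says of the 40 mg predictions: "These exposures are 4.2-fold (C_{max}) and 4.0-fold (AUC_{0-24}) below the exposure caps defined above". That implies caps of 285 × 4.2 = 1,197 nM and 2,850 × 4.0 = 11,400 nM*h, whereas 657/285 = 2.31 and 6,201/2,850 = 2.18. The public text therefore does not fix the maximum acceptable exposure.

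**The case against.** The strongest reply is that context favours the gMean-only reading. 'In this case' is singular and follows the gMean clause, its proviso tests expected gMeans, and the next sentence explains how the estimate is made. This stands: the narrow reading is plausible and may be intended. It still has to be inferred, and it does not settle the case where both triggers fire.

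A reader might infer a direct numerical contradiction between #6 and 1.4.3. The documents do not establish one. In 1.4.3 the two figures are stated as gMean limits in one sentence, and the individual stop comes in the next, worded as the maximum acceptable exposure. Equating the two is the most natural reading, but the defining section is not public. If the limit were 1,197 nM and 11,400 nM*h, neither example would trigger 1.4.3, and a clash at 20 mg would need 1,197/142.5 = 8.4 or 11,400/1,425 = 8.0 times predicted exposure. Also, 1.4.3 states no exception for the gMean trigger either, and 1.3.3.2 points to 3.3.4.3 for details, so the shorter statements may be summaries. The ambiguity within #6 does not depend on any of this, because #6 gives its own figures.

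A reader might also infer that nothing else would prevent the step. That is not so. Section 3.1 requires a documented safety review and a joint decision by the Principal Investigator and the Clinical Trial Leader, and an added dose group needs an amendment. Section 3.1 also allows the next group only "if none of the pre-specified trial-specific stopping criteria have been met". Read strictly, however, that condition would void the exception for both triggers, so it cannot show which one was meant. Lastly, 'lower than the planned next level' also covers doses below 20 mg, which are no escalation; but it does not exclude 30 mg.

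**Conclusion.** The point holds as an ambiguity in a mandatory safety rule and is worth a cheap correction. On the broad reading, #6 allows an upward step after an individual breach, with only a group-mean condition on exposure. The protocol's other statements of the single-subject stop mention no such exception. On either reading the planned next level is blocked.

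The practical reach is small unless the drug behaves unlike the prediction: about 0.1% or less at predicted exposure with two on active drug. The larger figures, up to 20%, combine twice-predicted exposure, an assumed gCV of 50% and all six subjects. They rest on log-normal Cmax, linear kinetics and variability that the documents do not give. Well-above-prediction exposure is nevertheless the situation the rule is there for. Confidence is medium, because the intended reading cannot be confirmed from the public text.

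**What to change.** In 3.3.4.3, criterion #6, replace 'In this case' with: *If only the expected gMean criterion is met and no subject has exceeded either threshold*. A single-subject exceedance then stops any further dose increase, including when both triggers fire. Doses at or below those already tested remain possible, since giving them is not escalation; a short added sentence could say so.

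The change needs no extra subjects, samples or procedures. The cost is that an intermediate dose such as 30 mg is lost after one outlier at 20 mg. If the sponsor does intend the exception to cover an individual breach, #6 should say so, and 1.3.3.1, 1.3.3.2, 1.4.3 and 3.1 should be aligned with it.
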